### Inclusion Criterion

1. Meets DSM-IV criteria for cannabis dependence, with at least 5 days of use per week over the past 30 days and displaying at least one positive utox during screening

Method of Ascertainment: MINI, psychiatry interview, self-report, utox

2. Physically healthy

Method of Ascertainment: Laboratory tests (urinalysis, blood chemistry, 12-lead ECG within normal limits, TB test), physical examination, self-reported medical history

3. No adverse reactions to study medications

Method of Ascertainment: Subjects will be asked about previous exposure to ketamine and midazolam

4. 21-60 years of age

Method of Ascertainment: Self-reported age, verification with legal identification

5. Capacity to consent and comply with study procedures

Method of Ascertainment: A short written test about study procedures, MINI, psychiatric interview

6. Seeking treatment

Method of Ascertainment: Psychiatric interview, self-report

Create or insert table to describe the exclusion criteria and methods to ascertain them

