## Study Procedures

Describe the procedures required for this study

Design: 15 patients meeting study criteria and providing informed consent will be entered into the 6-week trial, provided behavioral treatment, and given ketamine.

At each visit, patients will provide a urine sample that will be tested semi-quantitatively for cannabis and other drugs; complete various questionnaires; and undergo a brief evaluation during which vital signs, other safety parameters, and side effects are assessed. Two visits a week will be devoted to receiving behavioral treatment, lasting approximately 50 minutes. The other regular visit will be with a psychiatrist who will review progress, document self-reported substance use, and review side effects or other adverse events to treatment; additionally, the psychiatrist is responsible for the medical care of the patient and for decisions pertaining to study discontinuation.

There are two phases:

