### Phase 2 (Week 3-6)

During the last 4 weeks, patients will begin a standardized course of mindfulness based relapse prevention (MBRP); this training will occur twice a week, and take approximately one hour a session. Alongside MBRP training, patients will meet with a psychiatrist, who will continue monitoring their drug use and side effects.

In week 3 or 4, the patients will receive a second intravenous dose of ketamine (see “Infusion Procedures”) if they have been unable to attain abstinence. Before the scheduled infusion, an MET session will revisit goals and address ambivalence.

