**Infusion Procedures:** One or two ketamine infusions will take place at the BSU within the Division on Substance Abuse. Further, studies with depression have suggested that a single dose has (antidepressant) efficacy. Thus, for the purposes of this study, a single infusion may suffice to affect the outcome measures. If it does not suffice, patients will undergo a second infusion. Patients will be abstinent from intoxicants and will have not eaten since midnight prior to the infusion so as to reduce the risk of nausea, adverse interactions, and aspiration. Participants will be informed throughout the study that they may receive any of a number of substances at the infusion, including buspirone, d-cycloserine, ketamine, midazolam, memantine, saline, or any combination of these. This will serve to further disguise the administration of ketamine, and thereby further minimize the risk that patients will subsequently seek out ketamine. Ketamine hydrochloride (0.11 mg/kg 2-min bolus followed by 0.6 mg/kg over 50 minutes **for the first infusion** and 1.3 mg/kg over 90 minutes **for the second infusion**), will be prepared and packaged for slow-drip infusion by the pharmacy at NYSPI, and will be administered at 12 pm by a physician. The dose of ketamine was selected on the basis of published reports suggesting that it was sub-anesthetic and well-tolerated; it is also comparable to the dose used in the depression studies. Infusions will take place in the presence of an ACLS and BLS certified psychiatrist ([name]) who will remain available for up to two hours after the infusion is terminated and who will provide a brief safety and psychiatric evaluation at the end of the monitoring period. Blood pressure and heart rate will be monitored every five minutes beginning five minutes before the infusion and continuing after the infusion until vital signs normalize; SBP elevation > 60 mm and DBP > 40, or absolute SBP>200 and DBP>115 and HR > (220 – age) X 0.85, will result in infusion discontinuation (please see “Risks” for more information about managing BP or HR). The physician will also be responsible for decisions pertaining to the discontinuation of the infusion in the case of an adverse event. The physician will also be guiding mindfulness-based exercises for the duration of the infusion. A Clinician Administered Dissociative States Scale (CADSS) will be administered following the infusion by the physician or the staff. Ketamine and norketamine (an active metabolite) levels will be obtained at 30 minutes into the infusion and at 60 minutes (20 minutes after the infusion is terminated), the results of which will remain unavailable to all staff for each participant until all assessments are complete. The infusion will be preceded by a urine toxicology to ensure the absence of illicit substance use to minimize the risk of adverse interactions. Female participants will also be tested for pregnancy. Following the infusion, participants will undergo close monitoring, and prior to discharge (occurring at least 3 hrs post-infusion) psychiatric/medical clearance and a field sobriety test.

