There is a risk of adverse interactions with the study medications if participants are actively intoxicated on illicit medications. In order to minimize this risk, participants are encouraged to remain abstinent before the infusion, and will be tested daily with urine toxicology. They will also undergo a field sobriety test on the day of the infusion, prior to administration. In addition, they will be evaluated by a clinician ([name]) for DSM-IV signs of any intoxication.

In conclusion, the careful evaluation of participants during the screening process for cardiovascular, psychiatric, medical, and historical vulnerabilities to ketamine infusion; the presence of a psychiatrist with ACLS certification (the PI) during and after the infusion who will monitor for side effects and adverse events; the sub-anesthetic, generally well-tolerated dose at which ketamine will be infused; the close monitoring during infusion; the psychiatric evaluation and clearance to go home; the regular outpatient visits to monitor for persistent effects; and the provision of supportive and pharmacological measures to

address any side effects all ensure that the medical and psychiatric risks involved in participation in this study will be minimal.

2. Blood drawing/Intravenous placement: Another risk in the study is that bruising or a blood clot could form at the site of the intravenous line or venipuncture. Medical staff with extensive experience with IV placement will remain available to ensure that risks are minimized.

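### The pre-infusion urine check is written without a cannabis exception for near-daily cannabis users asked to stop at most 24 hours earlier, and the risk section sets a different standard

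*Protocol*

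**What the plan says.** All references are to the Protocol.

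- **Infusion Procedures** (under Phase 2): "Patients will be abstinent from intoxicants and will have not eaten since midnight prior to the infusion". Later in the same paragraph: "The infusion will be preceded by a urine toxicology to ensure the absence of illicit substance use", the stated reason being to lower the risk of interactions. The paragraph gives no cannabis exception, no cut-off and no consequence of a positive result.
- **Study Procedures**: the urine sample given at each visit is "tested semi-quantitatively for cannabis and other drugs".
- **Inclusion Criterion 1**: participants are cannabis dependent, "with at least 5 days of use per week over the past 30 days and displaying at least one positive utox during screening".
- **Phase 1 (Week 1-2)**: participants are asked to begin abstinence 24 hours before the drug is given. The next sentence puts the infusion on the day abstinence begins, and the Lay Summary also gives the same day.
- **Phase 2 (Week 3-6)**: a second infusion is given to participants "if they have been unable to attain abstinence". The Procedures (by week) table marks abstinence again at 3B, the column of the second infusion.
- **Risks/Discomforts/Inconveniences**: the stated hazard is active intoxication. To limit it, "participants are encouraged to remain abstinent before the infusion, and will be tested daily with urine toxicology". A field sobriety test before administration and a clinician's evaluation for signs of intoxication are added.
- **Specific Aims and Hypotheses**: the primary purpose is to learn whether one or two infusions are feasible in cannabis users.

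**The concern.** The check is written in terms of absence of use, and the people to be checked are enrolled because they use cannabis nearly every day. Little time is allowed between the request to stop and the test. The second infusion is reserved for people whose use has continued in some form. The risk section then describes the same safeguard in terms of intoxication, which is a different standard.

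Two staff members could therefore read the same cannabis-positive urine in opposite ways and both claim to follow the protocol. In a study of about 15 completers whose purpose is feasibility, that choice could decide who is infused. It also decides whether a protection described to the ethics board operates in the form described.

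**Working it through.** This is mainly a comparison of passages. No power or effect-size calculation enters it.

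**Step 1. Is cannabis within the check?** The study's urine test includes cannabis (Study Procedures). The risk section lists cannabis among drugs of abuse. Nothing in the Infusion Procedures takes it out. As written, it is included.

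**Step 2. How long is the pause before the first infusion?**

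| Source | Pause implied |
|---|---|
| Phase 1, first statement | 24 h |
| Phase 1, second statement; Lay Summary | same day, so less than 24 h |
| Infusion Procedures, if the midnight mark governs intoxicants as well as food (the sentence leaves this open) | midnight to 12 pm = 12 h |

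The pause is at most 24 h, and the protocol does not fix it at one value.

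**Step 3. When does the check conflict with the pause?** Let D be the urinary detection window and g the pause. For a participant who used cannabis up to the request to stop, the urine is positive at infusion if D > g. The protocol does not give D, so the values below are assumptions.

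| Assumed D | D > 24 h? | First infusions failing a literal check |
|---|---|---|
| Shorter than the actual pause | no | none on this ground |
| 2 days (48 h) | yes | up to 15 of 15 |
| 7 days (168 h) | yes | up to 15 of 15 |
| 21 days (504 h) | yes | up to 15 of 15 |

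The figure 15 of 15 is an upper bound. It requires every participant to have used up to the request to stop.

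**Step 4. Second infusion.** The trigger is failure to attain abstinence; the precondition is abstinence at the time of infusion. The table's abstinence mark at 3B shows a renewed attempt, so a participant can meet both. The length of that pause, g₂, is not stated. The condition is again D > g₂, with neither quantity given.

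**Step 5. What could the sample size absorb?** Description of Subject Population, Sample #1 plans 20 enrolled for 15 completers. At most 20 − 15 = 5 can be lost for any reason, and 5/20 = 25%. Suppose a literal check blocked the first infusion in a share p, with no other loss. The number infused is then binomial with n = 20 and probability 1 − p. The values of p are assumptions; the documents give no positivity rate.

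| p | Expected infused, 20(1 − p) | P(at least 15 infused) |
|---|---|---|
| 5% | 19 | 0.9997 |
| 10% | 18 | 0.989 |
| 25% | 15 | 0.617 |
| 50% | 10 | 0.021 |
| 75% | 5 | < 0.001 |

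**Step 6. Two standards side by side.** The Infusion Procedures state abstinence as a fact and aim the urine test at absence of use. The risk section encourages abstinence and aims at intoxication. It also speaks of daily urine tests, whereas Study Procedures and the weekly table tie urine collection to scheduled visits.

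**The case against.** The strongest defence is that the sponsor never meant a cannabis-positive urine to cancel an infusion. The risk section names active intoxication as the hazard and adds a sobriety test and a clinician's evaluation, and the urine test is semi-quantitative and repeated. Urine may therefore be one input to a physician's judgement. No passage says that a positive result cancels the infusion. This reading is open, so a reader who infers that the check must either block infusions or be ignored goes too far. If cannabis were set aside, the test would still screen for other drugs and the two other checks would remain. But the protocol does not state this reading, and it does not match the purpose given in the Infusion Procedures.

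Four other stronger inferences are not supported:

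- *The second-infusion trigger contradicts the check outright.* It does not. The abstinence mark at 3B lets failure to attain abstinence coexist with abstinence at infusion, and a conflict needs the same unstated detection window.
- *The test cannot tell use before the quit date from use after it.* The documents do not show this for a semi-quantitative test repeated at each visit.
- *A strict check would show infeasibility.* The stated primary outcome is tolerability, and no proportion infused is defined as an outcome. The link to the feasibility purpose is reasonable, but it is an inference.
- *Daily testing is impossible.* The table has three urine points in each infusion week and does not say that they are non-consecutive; one figure is not shown. What can be said is that daily testing is promised in one place and not scheduled in another.

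**Conclusion.** The point holds as an inconsistency in a stated safeguard. From the text alone, the check covers cannabis, the participants are near-daily users, the first pause is at most 24 hours and is described in more than one way, and the risk section applies a different standard from the Infusion Procedures.

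The size of the consequence rests on an assumption. If urine stays cannabis-positive for longer than the pause, a literal check stops infusions, up to all first infusions and an unknown share of second ones. The plan can lose no more than 5 of 20. If the window is shorter than the pause, there is no conflict. If the check is not applied to cannabis, the safeguard in the Infusion Procedures does not operate as written, although the risk section's other checks still do. The matter should be corrected, because it bears on who is infused in a feasibility study.

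**What to change.** Reconcile Phase 1, Phase 2, the Infusion Procedures and the risk section so that:

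1. one standard states whether a cannabis-positive pre-infusion urine bars the infusion, separately for the first and the second infusion;
2. the abstinence interval before the first infusion is given once and used consistently in Phase 1, the Lay Summary and the Infusion Procedures, and the interval before the second infusion is stated;
3. the risk section's daily testing is aligned with the urine collections in Study Procedures and the weekly table.

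The sponsor chooses the clinical rule; none is proposed here. The cost is protocol wording, with no new test needed.

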**Motivational Enhancement Therapy (MET):**

All patients will receive five MET sessions with a therapist over the first two weeks. Staff involved in MET will receive a 3-hour training in MET prior to providing therapy to participants, and a psychiatrist is available during all sessions for support or consultation in case it is needed. The psychiatrist will also see participants briefly following the therapy session before they go home. Staff will receive weekly supervision from the PI for the duration of the trial.

**Mindfulness-Based Relapse Prevention (MBRP):**

All patients will have eight MBRP sessions with therapists using a structured MBRP manual adapted for the purposes of this study to the individual setting, in collaboration with one of its lead authors, who will also be guiding efforts to ensure manual fidelity. Staff involved in mindfulness training receive a 3-hour training in MBRP prior to providing training to participants, and a psychiatrist is available during all sessions for support or consultation in case it is needed. The psychiatrist will also see participants briefly following the mindfulness training session before they go home. Staff will receive weekly supervision from the PI for the duration of the trial.

Procedures (by week)		1	2	2	2	3	3	3	4	5	6	E
			A	B	C	A	B	C				
ACTIVITY	Infusion*			X			X					
	MET	X	X	X		X	X					
	Abstinence			X			X					
	MD meet	X	X	X	X	X	X	X	X	X	X	X
	MBRP				X			X	X	X	X	
ASSESSMENT	TLFB	X	X	X	X	X	X	X	X	X	X	X
	VAS, CCQ	X	X	X	X	X	X	X	X	X	X	X
	FFMQ	X			X			X		X	X	X
	U-tox	X	X	X	X	X	X	X	X	X	X	X
	BPRS(+)			X			X					
	Battery			X			X					
	CADSS			X			X					
	(Nor)Ket			X			X					
	PSS	X			X			X	X	X	X	X
	DCQ	X			X			X	X	X	X	X
	BIS	X			X			X	X	X	X	X
	DES				X			X				
	Hood			X			X					
CGI			X	X	X	X	X	X	X	X	X	
Safety			X	X	X	X	X	X	X	X	X	

You can upload charts or diagrams if

any

## Criteria for Early Discontinuation

### Criteria for Early Discontinuation

Patients may elect to drop out at any time, and they may be removed by the treating clinicians for clinical reasons, including 1) clinically significant worsening leading to an acute psychiatric emergency (e.g., suicidality, psychosis, mania), or **2 or more weeks of moderately significant worsening (ascertained by a clinical evaluation following 2 weeks of a score of at least 6 or 7 on the CGI improvement scale. A score of 6 or 7 would lead to a clinical evaluation and then clinical judgment as to whether the patient should be discontinued);** 2) **inability to comply with study procedures prior to to the 1st infusion;** or 3) medical complications of treatment. Patients who terminate due to medical or psychiatric problems will be offered the necessary level of care (e.g., psychiatric hospitalization for psychosis, inpatient detoxification and rehabilitation for worsening drug use). **Due to the risks to pregnant women and their unborn children associated with these medications, becoming pregnant would result in a participant's early discontinuation from the study.**

## Blood and other Biological Samples

Please create or insert a table describing the proposed collection of blood or other biological specimens. Two vials of blood will be drawn during the screening process amounting to 10 cc ( $\frac{3}{4}$  tbsp). This is to determine if there are abnormalities that preclude enrollment into the study. The tests to be run are CBC, chem.-20 with LFTs, and b-HCG (for females). During the study, ketamine and norketamine levels will be obtained  $\frac{1}{2}$  hour into the infusion and 20 minutes after it is terminated; samples are frozen at -20 C and packaged in dry ice before being sent to the Nathan Kline lab. These samples will require about 10 cc (1 tbsp).

## Assessment Instruments

Create a table or give a brief description of the instruments that will be used for assessment

**Interviews:** Mini International Neuropsychiatric Interview (MINI): A semi-structured diagnostic interview designed to assist researchers in making reliable DSM-IV psychiatric diagnoses (45 min); Clinician Administered Dissociative States Scale (CADSS): A 23 item clinician administered instrument used to measure current dissociative symptoms (5 min); Dissociative Experiences Scale (DES): A 28 item questionnaire for assessing the extent of daily dissociative experience, modified to be administered by a clinician (5 min); Brief Psychiatric Rating Scale (BPRS) for positive symptoms: A 4 item subscale for assessing psychosis (1 min); Hood Mysticism Scale (HMS): a 32 item scale for assessing infusion-dependent mystical experience, modified to be administered by study staff (5 min); Five Facet Mindfulness Questionnaire (FFMQ): A 39 item instrument modified to be clinician administered that assesses five mindfulness domains: observing, describing, acting with awareness, non-judging of inner experience, and

non-reactivity (5 min); Timeline Follow-Back (TLFB): a retrospective method of quantifying daily consumption of alcohol and other drugs, assisted by the maintenance of a weekly use diary (5 min); Barratt Impulsiveness Scale (BIS): a 30 item questionnaire used to assess impulsivity, modified to be administered by a clinician (5 min); Adverse Symptom Report (ASR): At each visit, the presence, date of onset, or resolution of adverse effects will be queried and recorded; Clinical Global Impression Scale (CGI): The CGI severity and improvement scales measure the overall clinical status of the subjects and change from baseline; Hamilton Depression Scale (HAM-D): A 21 item instrument used to measure current depressive symptoms; Treatment Service Review (TSR): A 8 item questionnaire that assesses the recent exposure of participants to treatment obtained in the community in excess of what is provided in this protocol; Childhood Traumatic Events Scale (CTES): A 6 item semi-structured interview that assesses childhood trauma prior to age 17.

**Self-Reports:** Psychiatric Epidemiology Research Interview Life Events Scale (PERI): A 102 item self-report that evaluates possible traumas that a participant may have experienced in his/her life in the past 6 months; Drug-Taking Confidence Questionnaire (DCQ): A validated assessment of self-efficacy; Alcohol Abstinence Self-Efficacy Scale: a 40-item assessment that assesses confidence to stop using alcohol in various situations (5 min); Perceived Stress Scale (PSS): A 9 item scale that measures levels of subjective stress, modified from a monthly assessment to one that evaluates stress between visits (5 min); VAS for alcohol craving (VAS-A): A 10 cm long line from “not at all” to “extremely” to assess craving intensity and frequency (1 min). Temperament and Character Inventory (TCI): 240 item questionnaire evaluating 4 temperament and 3 character dimensions.

**Physiological Measures:** Blood pressure and temperature.

Please attach copies, unless standard instruments are used

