## Background, Significance and Rationale

### Background, Significance and Rationale

This proposal will focus on treating cannabis use disorders with a one or two sub-anesthetic infusions of ketamine (0.11 mg/kg 2-min bolus followed by 0.6 mg/kg over 50 minutes or 1.3 mg/kg over 90 minutes), a high-affinity non-competitive N-methyl-D-aspartate receptor (NMDAR) antagonist. Our preliminary research suggests that ketamine improves dependence-related vulnerabilities common to a variety of substances. We have shown that a single infusion improves motivation to quit, reduces cue-induced craving, improves non-reactivity, and reduces cocaine self-administration among non-treatment cocaine dependent individuals. We have also shown that ketamine infusions can be integrated into outpatient behavioral treatment, such as motivational enhancement therapy (MET) and mindfulness-based relapse prevention (MBRP), to address cocaine use disorder and alcohol use disorder. This includes a protocol with cocaine users that provides up to 2 ketamine infusions. In these protocols, some individuals who had been using cannabis problematically in addition to the substance for which they sought treatment stopped using cannabis.

In this single blind, open label trial, we extend the treatment model we have developed to treat cocaine use disorder to the treatment of cannabis use disorder, with the expectation that we will observe similar feasibility. This protocol includes a manualized sequence of MET and MBRP in conjunction with up to 2 infusions of ketamine. The primary outcome is tolerability of study medications.

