## Description of Subject Population

### Sample #1

Specify subject population

Cannabis dependent individuals

Number of completers required to accomplish study aims

15

Projected number of subjects who will be enrolled to obtain required number of completers

20

Age range of subject population

21-60

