### Exclusion Criterion

1. Meets DSM IV criteria for current major depression, bipolar disorder, schizophrenia, any psychotic illness, including substance-induced psychosis, and current substance-induced mood disorder with HAMD > 12.

Method of Ascertainment: Psychiatric Interview, MINI, HAMD

2. Physiological dependence on another substance requiring medical management, such as alcohol, opioids, or benzodiazepines, excluding caffeine, and nicotine

3. Pregnant, interested in becoming pregnant, or lactating

Method of Ascertainment: Blood and urine pregnancy testing, self-report

4. Delirium, Dementia, Amnesia, Cognitive Disorders, or dissociative disorders

Method of Ascertainment: MINI, Psychiatric Interview

5. Current suicide risk or a history of suicide attempt within the past 2 years

Method of Ascertainment: MINI, Psychiatric Interview

6. On psychotropic or other medication whose effect could be disrupted by participation in the study

Method of Ascertainment: Psychiatric Interview, self-reported medical history

7. Recent history of significant violence (past 2 years).

Method of Ascertainment: MINI, Psychiatric Interview

8. Heart disease as indicated by history, abnormal ECG, previous cardiac surgery.

Method of Ascertainment: Laboratory tests (12-lead ECG in normal limits), physical examination, self-reported medical history

9. Unstable physical disorders which might make participation hazardous such as end-stage AIDS, hypertension (>140/90), anemia, pulmonary disease, active hepatitis or other liver disease (transaminase levels < 2-3 X the upper limit of normal will be considered acceptable), or untreated diabetes

Method of Ascertainment: Laboratory tests (urinalysis, blood chemistry, 12-lead ECG in normal limits, TB test), physical examination, self-reported medical history

10. Previous history of ketamine or benzodiazepine abuse, and/or a history of adverse reaction/experience with prior exposure to ketamine or benzodiazepines

Method of Ascertainment: MINI, Psychiatric Interview

11. BMI > 35, or a history of undocumented obstructive sleep apnea

Method of Ascertainment: Physical exam, self-reported medical history

12. First degree relative with a psychotic disorder (bipolar disorder with psychotic features, schizophrenia, schizoaffective disorder, or psychosis NOS)

Method of Ascertainment: MINI, Psychiatric Interview

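### The only VAS the protocol defines is for alcohol craving, and the CCQ scheduled beside it is undefined, so no defined instrument measures cannabis craving

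*Protocol*

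**What the plan says.** - **Population.** Description of Subject Population, Sample #1, gives the group as "Cannabis dependent individuals". The first inclusion criterion reads "Meets DSM-IV criteria for cannabis dependence, with at least 5 days of use per week over the past 30 days".
- **Alcohol.** The second exclusion criterion removes those with "Physiological dependence on another substance requiring medical management, such as alcohol, opioids, or benzodiazepines". Specific Aims and Hypotheses does not mention alcohol.
- **Craving VAS.** The self-report list under Assessment Instruments describes one VAS only: "VAS for alcohol craving (VAS-A): A 10 cm long line from", followed by its two end labels.
- **Self-efficacy.** The same list contains "Alcohol Abstinence Self-Efficacy Scale: a 40-item assessment that assesses confidence to stop using alcohol in various situations" and also "Drug-Taking Confidence Questionnaire (DCQ): A validated assessment of self-efficacy". The second entry names no substance.
- **Schedule.** The table of procedures by week, under Study Procedures after the MBRP description, has a single row for VAS and CCQ. It is marked in every column. The table also has a DCQ row, but none for the alcohol self-efficacy scale.
- **CCQ.** The abbreviation appears in that row and nowhere else in the text supplied.
- **Outcome.** Background, Significance and Rationale states: "The primary outcome is tolerability of study medications".

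**The concern.** A craving scale is useful here only if it asks about the drug being treated. The protocol gives no reason for asking cannabis users about alcohol craving, and alcohol is not a studied substance. The Background section says the treatment model was carried over from work in cocaine and alcohol use disorder, so text left over from another protocol is a plausible explanation, though not a documented one.

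At stake is a data stream planned for every scheduled time point. The Background section counts reduced craving among ketamine's effects in cocaine-dependent people and presents this trial as extending that model to cannabis. Alcohol ratings could not show whether craving for cannabis changes. Choosing the right substance is not a matter for later analysis, because no statistical analysis plan can change the question that participants were asked.

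**Working it through.** There is no sample size, power or error rate to reproduce. The check sets the instrument list beside the schedule and the population.

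1. **Instruments described.** Reading the interviews and self-reports in full, the only entry that measures craving is the VAS-A, and its substance is alcohol. No entry describes a scale for cannabis craving.

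2. **Instruments scheduled.** The schedule columns are 1, 2A, 2B, 2C, 3A, 3B, 3C, 4, 5, 6 and E, which makes 1 + 3 + 3 + 3 + 1 = 11. The VAS and CCQ row is marked in 11 of 11. Only two other assessment rows, TLFB and urine toxicology, are marked throughout.

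3. **Link between the two.** The schedule says VAS, not VAS-A. Since the VAS-A is the only VAS described, someone following the protocol has no other form to use. The link is therefore a reasonable inference, not a stated fact.

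4. **The CCQ.** It is not expanded, described or tied to a substance. It may concern cannabis, but the text does not say so. It can be counted neither as a cannabis measure nor as a second misdirected one.

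5. **Self-efficacy.** The alcohol scale has no schedule row, so no planned administration of it can be counted. The scheduled measure is the DCQ, which is not tied to alcohol but whose target drug is not given.

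6. **Scale.** For orientation, 11 columns × 15 completers = 165 schedule cells, and 11 × 20 projected enrolees = 220. Neither is a bound on the number of ratings. Columns 1, 4, 5 and 6 each stand for a whole week, in which Study Procedures describes more than one visit. The second infusion, shown in the week 3 columns, is conditional.

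7. **What is not touched.** Urine is tested for cannabis at each visit and TLFB records daily use of alcohol and other drugs, so cannabis use is still measured. Specific Aims and Hypotheses names feasibility as the purpose, and the stated primary outcome is tolerability. Neither depends on the craving scales.

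**The case against.** The strongest reply has four parts.

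- **The CCQ may cover cannabis craving.** This stands as a limit on the claim. A reader might infer that all the scheduled craving data concern the wrong substance in every participant. The documents do not support that, because a second instrument shares the row and its target is unknown. It is not a defence either: an undefined abbreviation is no evidence that cannabis craving is measured.
- **The schedule does not say VAS-A, and the forms are not shown.** This also stands. What participants would actually be asked cannot be confirmed, so the loss of data is conditional on the defined form being used.
- **The alcohol self-efficacy scale is not scheduled.** Correct. A reader might add it to the lost data, but the schedule shows no administration to lose. It remains a listed instrument with no stated use.
- **Craving is neither an aim nor the primary outcome.** Correct. The Lay Summary names mindfulness, impulsivity and stress sensitivity as the measures of mechanism, and the craving finding cited in the Background is cue-induced, which a routine visit VAS does not measure. This lowers the importance of the point but does not remove the mismatch.

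A reader might also expect alcohol ratings near the bottom of the scale. The exclusion removes only physiological dependence that needs medical management, not drinking, and the protocol gives no figures for alcohol use. No floor effect can be asserted.

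**Conclusion.** The point holds in this form: the protocol enrols cannabis-dependent participants, defines its only VAS for alcohol craving, schedules a VAS in all 11 columns, and leaves the accompanying CCQ undefined. No defined instrument measures cannabis craving. This is an instrument specified for the wrong substance, not detail deferred to another document.

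The consequence rests on one assumption, that the scheduled VAS is the one described. If so, the VAS ratings say nothing about cannabis craving, and the cannabis ratings that were not taken cannot be reconstructed. If the form in use is already worded for cannabis, the fault is confined to the protocol text.

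The size is modest. A secondary assessment is affected; the feasibility aim, the tolerability outcome and the measurement of cannabis use are not. The correction should be made because it costs almost nothing and cannot be made after the visits.

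**What to change.** - In the self-report list under Assessment Instruments, word the same 10 cm VAS for cannabis craving, or state why alcohol is intended.
- Make the schedule and the instrument list agree: use one name for the VAS in both, expand and describe the CCQ, and state its target substance. The sponsor must supply this, as it cannot be presumed from the text.
- Name cannabis as the target drug of the DCQ.
- Delete the Alcohol Abstinence Self-Efficacy Scale, or justify it and add it to the schedule.
- Check the forms in use against the corrected text.

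The cost is an edit to the instrument paragraph, the schedule and the forms. It needs no extra visits, staff or participants.
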